6.1.4.2 Evaluation of Non-Target Lesions

Complete Response (CR): Disappearance of all non-target lesions and normalization of tumor marker level. All lymph nodes must be non-pathological in size (< 10 mm short axis).

Incomplete Response/Stable Disease (SD): Persistence of one or more non-target lesion(s) and/or maintenance of tumor marker level above the normal limits.

Progressive Disease (PD): Appearance of one or more new lesions and/or unequivocal progression of existing non-target lesions

6.1.4.3 Evaluation of Best Overall Response

The best overall response is the best response recorded from the start of the treatment until disease progression/recurrence (taking as reference for progressive disease the smallest measurements recorded since the treatment started). The subjects' best response assignment will depend on the achievement of both measurement and confirmation criteria.

Target Lesions	Non-Target Lesions	New Lesions	Overall Response	Best Response for this Category Also Requires:
CR	CR	No	CR	≥4 wks. confirmation
CR	Non-CR/Non-PD	No	PR	≥4 wks. confirmation
PR	Non-PD	No	PR	
SD	Non-PD	No	SD	Documented at least once ≥4 wks. from baseline
PD	Any	Yes or No	PD	no prior SD, PR or CR
Any	PD*	Yes or No	PD	
Any	Any	Yes	PD	

* In exceptional circumstances, unequivocal progression in non-target lesions may be accepted as disease progression.
 
Note: Subjects with a global deterioration of health status requiring discontinuation of treatment without objective evidence of disease progression at that time should be reported as “symptomatic deterioration”. Every effort should be made to document the objective progression even after discontinuation of treatment.
				

Note: If subjects respond to treatment and are able to have their disease resected, the patient’s response will be assessed prior to the surgery.

6.1.4.4 Evaluation of Bone Lesions:

Bone lesions will be evaluated either by CT or MRI, whichever is deemed to be better suited by baseline studies. Since the size of the lesion is difficult to measure in a bone scan, particularly if it is not well visible in CT, the following guideline will be used. Any ambiguity will require MRI for resolution:

6.1.4.4.1 Progression of bone lesions will be defined as follows:

- Appearance of 1 or more new bone lesion in CT scan, confirmed by a repeat scan in ≥6 weeks.

6.1.4.4.2 Response of bone lesions in CT scan will be defined by either a complete resolution (CR) at the metastatic sites or partial resolution (PR) of radiotracer uptake by a radiologist.

6.1.4.5 Evaluation of Pathologic Fracture:

Any clinical suspicion of pathologic fracture will prompt radiologic evaluation with plain film, CT or MRI as appropriate and if confirmed by a radiologist, will constitute progression, unless it is at a treated site, in which case a treatment-related toxicity will be considered. In that case, patients will be referred for orthopedics specialist evaluation.

6.1.4.6 Evaluation of spinal cord Compression or Cauda Equina compression:

Any clinical suspicion of cord or cauda equina compression will prompt radiologic evaluation with MRI (CT myelography if patient is not eligible for MRI) as appropriate and if confirmed by a radiologist, will constitute progression.

6.1.5 Response Rate:

Response rate (RR) is defined by combining CR and PR.

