6.1.2 Disease Parameters

Measurable disease. Measurable lesions are defined as those that can be accurately measured in at least one dimension (longest diameter to be recorded)

as ≥ 10 mm with spiral (Helical) CT scan (CT/MRI scan slice thickness should be no greater than 5 mm). All tumor measurements must be recorded in millimeters (or decimal fractions of centimeters). For malignant lymph nodes to be considered pathologically enlarged and measurable, a lymph node must be ≥ 15 mm in short axis when assessed by CT scan (CT scan slice thickness recommended to be no greater than 5 mm). At baseline and in follow-up, only the short axis will be measured and followed. Bone scan, PET scan or plain films are not considered adequate imaging techniques to measure bone lesions. However, these techniques can be used to confirm the presence or disappearance of bone lesions. Lytic bone lesions or mixed lytic-blastic lesions, with identifiable soft tissue components, that can be evaluated by cross sectional imaging techniques such as CT or MRI can be considered as measurable lesions if the soft tissue component meets the definition of measurability described above.

Non-measurable disease. All other lesions (or sites of disease), including small lesions (longest diameter < 20 mm with conventional techniques or < 10 mm using spiral CT scan) and lymph nodes < 15 mm, are considered non-measurable disease. Leptomeningeal disease (patients excluded), ascites, pleural/pericardial effusions, lymphangitis cutis/pulmonis, inflammatory breast disease, abdominal masses (not followed by CT or MRI), and cystic lesions are all non-measurable. Blastic bone lesions are non-measurable. Lesions that meet the criteria for radiographically defined simple cysts should not be considered as malignant lesions (neither measurable nor non-measurable) since they are, by definition, simple cysts. 'Cystic lesions' thought to represent cystic metastases can be considered as measurable lesions, if they meet the definition of measurability described above. However, if non-cystic lesions are present in the same subject, these are preferred for selection as target lesions.

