6.1.3 Methods for Evaluation of Measurable Disease

All measurements will be done digitally on the PACs system. All baseline evaluations should be performed as closely as possible to the beginning of treatment.

Whenever possible, the same method of assessment and the same technique should be used to characterize each identified and reported lesion at baseline and during follow-up using appropriate radiologic imaging.

MRI Brain, and CT scan or MRI with IV contrast (whenever possible) will be performed at baseline. Since bone scan is not reliable for RCC, it will only be used to evaluate overall response when positive in baseline scan, and any new lesions found on bone scan must be verified with a CT. Bone scans will not be used for measuring lesion size.

Spiral CT and MRI. All CT scans will be Spiral CT and should be performed using a 5 mm contiguous reconstruction algorithm.

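### Section 6.1.4.4.2 defines partial response of bone lesions on CT by radiotracer uptake, which CT does not measure and which conflicts with the rest of section 6.1

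*Combined protocol and SAP*

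**What the plan says.** Section 6.1 bases the primary endpoint on RECIST v1.1 and states that extra criteria for bone lesions are added through section 6.1.4. Section 6.1.5 defines response rate as CR and PR combined.

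For bone, section 6.1.4.4 first names the modality: "Bone lesions will be evaluated either by CT or MRI, whichever is deemed to be better suited by baseline studies". Section 6.1.4.4.2 then gives the response rule: "Response of bone lesions in CT scan will be defined by either a complete resolution (CR) at the metastatic sites or partial resolution (PR"). The PR branch is worded as "partial resolution (PR) of radiotracer uptake by a radiologist". It gives no threshold for the reduction and names no tracer study.

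Other parts of section 6.1 bear on the same lesions:

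- Section 6.1.2: "Bone scan, PET scan or plain films are not considered adequate imaging techniques to measure bone lesions". The next sentence allows a limited role: "However, these techniques can be used to confirm the presence or disappearance of bone lesions".
- Section 6.1.2 also lets lytic or mixed lytic-blastic lesions count as measurable if they have a soft-tissue component that meets the size definition on CT or MRI. Blastic lesions are non-measurable.
- Section 6.1.3: "Since bone scan is not reliable for RCC, it will only be used to evaluate overall response when positive in baseline scan". It adds: "Bone scans will not be used for measuring lesion size".
- Section 6.1.4.1 defines PR of target lesions as a fall of at least 30% in the sum of longest diameters.
- Section 6.1.4.2 gives non-target lesions three categories (CR, incomplete response/SD, PD) and no PR.
- The Time and Events table (5.4) schedules CT, with MRI as an alternative, and no bone scan or PET.

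**The concern.** As written, the PR branch of 6.1.4.4.2 cannot be applied: it asks a radiologist to judge on CT a quantity that CT does not record. A reader who tries to make it work has to choose between ignoring it and using a tracer scan that 6.1.2 calls inadequate for measuring bone lesions. Two readers following different paragraphs of section 6.1 could give the same patient different responses.

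The clause matters because it sits inside the definition of the primary endpoint. With 19 evaluable patients in a single-arm trial whose tumour assessments are made by the investigator (section 5.3), a few responses called on an unthresholded visual criterion can change the conclusion.

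**Working it through.** **1. Can the rule be rescued by another reading?** Suppose the reference to CT is a slip for bone scan or PET. Section 6.1.4.4 itself mentions the difficulty of measuring size on a bone scan, so this is plausible. The rule then has a measurable quantity, but it still conflicts with 6.1.2, where these scans may confirm only presence or disappearance. A partial fall in uptake is neither. Section 5.4 also schedules no tracer scan, so serial uptake would not be routinely available.

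**2. Where could the rule reach the primary endpoint?** The best-overall-response table in 6.1.4.3 gives an overall PR in two ways: target lesions in PR with non-target lesions not in PD, or target lesions in CR with non-target lesions short of CR and not in PD.

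- *Non-target bone lesion.* A partial change falls in the non-CR/non-PD category. It does not by itself produce an overall PR.
- *Bone lesion with measurable soft tissue, chosen as a target.* Two PR rules now apply to one lesion: the 30% diameter rule of 6.1.4.1 and the uptake wording of 6.1.4.4.2. Inclusion criterion 3.1.4 asks for only one measurable non-radiated site, so such a lesion could be the patient's only target lesion.
- *Reader outside the table.* Section 6.1 describes the bone criteria as added, and 6.1.4.4.2 does not say how its PR feeds the table. A reader could take it as a stand-alone route to PR.

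Only the second and third routes carry risk.

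**3. The plan's own design figure.** Inputs from section 11.2: 19 patients, 25% versus 50%, exact binomial test, two-sided level 0.2 (0.10 in the upper tail), 80% power. With

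P(X ≥ r | n, p) = Σ from k = r to n of C(n,k) p^k (1 − p)^(n − k),

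the smallest r at n = 19 with an upper tail of at most 0.10 under p = 0.25 is r = 8:

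- P(X ≥ 8 | 19, 0.25) = 0.0775
- P(X ≥ 7 | 19, 0.25) = 0.1749, so 7 is too low
- P(X ≥ 8 | 19, 0.50) = 0.8204

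Every n from 10 to 18 has power below 0.80 (n = 18: 0.7597), so the plan's 19 is reproduced. The boundary of 8/19 is implied by the stated test; the plan does not print it.

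**4. Sensitivity to miscalled responses.** One patient is 1/19 = 5.3 percentage points of response rate. Let f be the share of true non-responders wrongly called PR. The documents give no rate, so f is an assumption. At a true rate of 25% the apparent rate is p = 0.25 + 0.75f.

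| f | apparent p | P(X ≥ 8 of 19) |
|---|---|---|
| 0 | 0.2500 | 0.078 |
| 2% | 0.2650 | 0.103 |
| 5% | 0.2875 | 0.151 |
| 10% | 0.3250 | 0.253 |
| 15% | 0.3625 | 0.378 |

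The upper-tail level of 0.10 is already passed at f = 2%. The table shows how sensitive the test is to any such miscall; it does not estimate how often this clause would cause one.

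**The case against.** The strongest reply is that the response table already closes most of the route. Overall PR needs target-lesion PR or CR, target lesions are judged by diameter, non-target lesions have no PR category, and every patient must have measurable non-radiated disease. Bone-only, non-measurable disease therefore cannot decide a patient's response. This stands, and it limits the point to the two routes in step 2.

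The plan also does not ban tracer imaging. Section 6.1.2 allows it to confirm presence or disappearance, and under 6.1.3 a bone scan may be used, in that "it will only be used to evaluate overall response when positive in baseline scan". Section 6.1.4.4 sends ambiguous cases to MRI, and the schedule collects no tracer scan. These facts stand too. They make extra responders less likely, but they leave a PR criterion that cannot be carried out with the scheduled imaging. The permission in 6.1.3 also sits uneasily with the narrower one in 6.1.2.

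A reader might infer that the clause raises the false-positive rate from 7.7% to 17.5%, by replacing the boundary of 8 with 7. The documents do not support that. It assumes one false PR in every trial that has exactly 7 true responders, and nothing in the plan gives the frequency of bone metastases, of tracer scans or of miscalls. A reader might also infer that all bone disease gains a PR category and feeds the response rate directly. The table in 6.1.4.3 rules that out for non-target lesions.

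**Conclusion.** Wrong as written. The PR rule in 6.1.4.4.2 names a quantity that its stated modality does not measure, sets no threshold, and disagrees with 6.1.2, 6.1.4.1, 6.1.4.2 and the opening of 6.1.4.4. Reading it as a bone scan or PET rule does not remove the conflict.

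The exposure of the primary response rate is real but limited to soft-tissue bone lesions used as targets and to readers who apply the bone rule outside the table. The number of patients affected cannot be derived. The scale is 5.3 points of response rate per miscalled patient. For assumed miscall shares of 0, 2% and 5% of non-responders, the chance of reaching 8/19 at a true rate of 25% is 0.078, 0.103 and 0.151. These figures rest on 19 evaluable patients and the boundary implied by section 11.2. The sample size itself is not in question.

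**What to change.** Replace 6.1.4.4.2 with a rule of three parts:

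- Bone lesions with a measurable soft-tissue component are assessed on CT or MRI under 6.1.2 and 6.1.4.1, by diameter, like any other measurable lesion.
- All other bone lesions are non-target, can be only CR, non-CR/non-PD or PD, and enter overall response only through the 6.1.4.3 table.
- Tracer uptake is not a criterion for PR. Bone scan or PET may only confirm presence or disappearance, as 6.1.2 already allows.

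Align the bone-scan sentence in 6.1.3 with the third part, so that a scan positive at baseline informs overall response only in that confirming role.

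The cost is one replaced paragraph and one edited sentence in a protocol amendment. It uses imaging already scheduled and changes neither sample size, visits nor treatment. If any bone response has already been called on uptake, it should be re-read under the new rule.

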6.1.6 Duration of Response

Duration of overall response: The duration of overall response is measured from the time measurement criteria are met for CR or PR (whichever is first recorded) until the first date that recurrent or progressive disease is objectively documented (taking as reference for progressive disease the smallest measurements recorded since the treatment started).

The duration of overall CR is measured from the time measurement criteria are first met for CR until the first date that recurrent disease is objectively documented.

Duration of stable disease: Stable disease is measured from the start of the study registration until the criteria for progression are met, taking as reference the smallest measurements recorded since the treatment started.

6.1.7 Progression-Free Survival

Progression-free survival (PFS) is defined as the duration of time from the date of registration to time of progression or date of death due to any cause.

6.2 Safety/tolerability

Analyses will be performed for all subjects having received at least one fraction of SABR and one cycle of Nivolumab. The study will use the CTCAE version 4.0 for reporting of non-hematologic adverse events (<http://ctep.cancer.gov/reporting/ctc.html>) and modified criteria for hematologic adverse events.

6.3 Quality of Life (QoL)**6.3.1 Functional Assessment of Cancer Therapy-P (FACT-G) and Kidney Symptom Index (FKSI)**

Patient-reported functional status will be assessed the Functional Assessment of Cancer Therapy-General (FACT-G) (See appendix E). The FACT-G is a 28-item questionnaire that uses 5-point Likert-type response choices (0 = not at all; 1 = a little bit; 2 = somewhat; 3 = quite a bit; 4 = very much). It will take less than 10 minutes to complete the questionnaire. The Trial Outcome Indices (TOI) also will be utilized to measure the summed functional well-being, and physical well-being [102, 103]. A 5-point deterioration in the FACT-G TOI between pre-treatment and at post treatment or at year 1 will be considered clinically significant [104].

The FKSI is a 15 question validated symptom index for kidney cancer patients which has been used in several metastatic renal cell cancer studies [105]. This scale focuses on symptoms predominantly related to kidney cancer such as energy, fatigue, pain, bone pain, weight loss, shortness of breath, cough, fever, hematuria. This subscale of the FKSI-DRS was validated in another study as well [106]. The FACT-G and FKSI will

be collected prior to first Nivolumab dose (baseline), and at every subsequent follow up appointment until the patient meets primary endpoint [105][3][82].

The first analysis of change in QOL from baseline to 8 weeks will only be performed on patients who are still alive at 8 weeks. Changes in QOL will be also analyzed using all available data at baseline, 2, 4, 6, 8, 10 and 12 months with semiparametric generalized estimating equations (GEE).

Additionally, similarly we will also compare the percentage of patients with an effect size for the change in FKSI (FKSI) scores between pre-treatment and post treatment which will allow us to compare the percentage of patients whose functional status remains more similar to baseline levels.

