2.0 STUDY OBJECTIVES

This study is a safety lead-in phase II single institution clinical trial using Nivolumab and concurrent SABR to 1-6 metastatic sites in patients with metastatic clear cell renal cell cancer (mccRCC) who have received at least one prior anti-angiogenic therapy. Nivolumab will be dosed intravenously as per the institution guidelines, until disease progression, unacceptable toxicity or other reasons specified in the protocol. No dose modifications for Nivolumab will be allowed. SABR will be administered to 1-6 sites of metastatic disease one week after the first dose of

Nivolumab with a single (24-27 Gy) or three (11-16 Gy/fraction) fractions. The sites of larger (bulky) disease and the sites of symptomatic disease will be prioritized for treatment at the discretion of the treating radiation oncologist.

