4.0 TREATMENT PLAN

4.1 SABR Dose and Techniques

Patients should have at least 1 measurable non-CNS lesions. Lesions receiving SABR will be called “radiated” lesions. “Target” lesions will be selected from non-treated lesions. In any case, there should be at least one (non-CNS) measurable lesion for effect measurement. Prior irradiated lesions (outside of the trial) will be excluded from target lesions. SABR will be administered to 1-6 sites of metastatic disease on the 2 weeks after the second dose of Nivolumab with a single (24-27 Gy) or three (11-16 Gy/fraction) fractions. The sites of larger (bulky) disease and the sites of symptomatic disease will be prioritized for treatment.

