4.2.1.1 Toxicities and Dosing Delays/Dose Modifications

Any subject who receives treatment on this protocol will be evaluable for toxicity. Each patient will be assessed for the development of toxicity according to the Time and Events table (5.4). Toxicity will be assessed according to the NCI Common Toxicity Criteria for Adverse Events (CTCAE), version 4.0. No dose modifications for Nivolumab will be allowed. Treatment with Nivolumab will be modified by withholding doses rather than continuing therapy at a reduced dose. We recommend to follow the FDA institutional guidelines or at the discretion of the treating medical oncologist for any dose delay criteria, criteria to resume treatment with Nivolumab and/or discontinuation for nivolumab.

Treatment of Nivolumab Related Infusion Reactions

Since Nivolumab contains only human immunoglobulin protein sequences, it is unlikely to be immunogenic and induce infusion or hypersensitivity reactions. However, if such a reaction were to occur, it might manifest with fever, chills, rigors, headache, rash, pruritus, arthralgias, hypo- or hypertension, bronchospasm, or other symptoms. All Grade 3 or 4 infusion reactions should be reported within 24 hours as an SAE if criteria are met. Infusion reactions should be graded according to NCI CTCAE (version 4.0) guidelines.

Treatment recommendations are provided below and may be modified based on local treatment standards and guidelines, as appropriate:

For Grade 1 symptoms: (Mild reaction; infusion interruption not indicated; intervention not indicated) Remain at bedside and monitor subject until recovery from symptoms. The following prophylactic premedications are recommended for future infusions: diphenhydramine 50 mg (or equivalent) and/or paracetamol 325 to 1000 mg (acetaminophen) at least 30 minutes before additional Nivolumab administrations.

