4.3 Duration of Therapy

Nivolumab will be dosed per standard of care approved guidelines. Nivolumab administration will be repeated, at the discretion of the treating medical oncologist until [5]:

- Disease progression as per the ir-RECIST criteria
- Inter-current illness that prevents further administration of treatment
- Unacceptable adverse event(s)
- Subject decides to withdraw from the study, **OR**
- General or specific changes in the patient's condition render the subject unacceptable for further treatment in the judgment of the principal investigator or medical oncologist.

SABR will be performed after the second Nivolumab dose but before the fourth dose (i.e. before the second Nivolumab cycles).

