5.5 Removal of Subjects from Study Treatment or Study

Subjects can be taken off the study treatment and/or study at any time at their own request, or they may be withdrawn at the discretion of the investigator for safety, behavioral or administrative reasons. The reason(s) for discontinuation will be documented and may include:

- 5.5.1 Subject voluntarily withdraws from treatment (follow-up permitted);
- 5.5.2 Subject withdraws consent (termination of treatment and follow-up);
- 5.5.3 Subject is unable to comply with protocol requirements; patients must be withdrawn from the trial and replaced if they failed to receive the SABR treatment. Any patient with at least one cycle of Nivolumab and SABR will be included in the analysis.
- 5.5.4 Subject demonstrates disease progression (unless continued treatment with Nivolumab is deemed appropriate at the discretion of the medical oncologist);
- 5.5.5 Subject experiences toxicity that makes continuation in the protocol unsafe;

- 5.5.6 Treating physician judges' continuation on the study would not be in the subject's best interest;
- 5.5.7 Subject becomes pregnant (pregnancy to be reported along same timelines as a serious adverse event);
- 5.5.8 Development of second malignancy (except for basal cell carcinoma or squamous cell carcinoma of the skin) that requires treatment, which would interfere with this study;
- 5.5.9 Lost to follow-up. If a research subject cannot be located to document survival after a period of 2 years, the subject may be considered "lost to follow-up." All attempts to contact the subject during the two years must be documented .

5.6. Subject Replacement: Subject replacements are allowed in the following situations:

- 5.6.1 If the subjects decide to withdraw from the study without finishing the course of SAbR
- 5.6.2 If the subjects decide to withdraw from the study or lost to follow up (for reasons of death from other causes, moving to other state etc.) or refuse follow up scans leading to <2 follow-up scans (making it impossible to assess the primary endpoint of the trial)

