6.1.1 Definitions

Evaluable for toxicity. All subjects will be evaluable for toxicity from the time of their registration.

Evaluable for objective response. Only those subjects who have undergone SABR and 1 cycle of Nivolumab and have had their disease re-evaluated at least at two occasions will be considered evaluable for response. These subjects will have their response classified according to the definitions stated below.

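### Section 6.2 limits the safety analyses to patients given both SABR and nivolumab, against 4.2.1.1 and 6.1.1, so a patient whose early nivolumab toxicity prevents SABR is left out of the analysed toxicity rate

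*Combined protocol and SAP*

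**What the plan says.** Three sections of the combined protocol and SAP say who counts for toxicity.

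- Section 6.2 (Safety/tolerability): "Analyses will be performed for all subjects having received at least one fraction of SABR and one cycle of Nivolumab".
- Section 4.2.1.1 (Toxicities and Dosing Delays/Dose Modifications): "Any subject who receives treatment on this protocol will be evaluable for toxicity".
- Section 6.1.1 (Definitions): "All subjects will be evaluable for toxicity from the time of their registration".

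Section 5.5.3 adds that "patients must be withdrawn from the trial and replaced if they failed to receive the SABR treatment", and then "Any patient with at least one cycle of Nivolumab and SABR will be included in the analysis", without saying which analysis is meant. Section 11.3 plans an exact binomial toxicity rate with a 95% confidence interval and does not name the patients it is computed on. Tolerability and toxicity is a secondary objective (2.2.7).

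The timing of SABR is described in several ways. Section 2.0 has "SABR will be administered to 1-6 sites of metastatic disease one week after the first dose of" nivolumab. Section 4.1 has "SABR will be administered to 1-6 sites of metastatic disease on the 2 weeks after the second dose of Nivolumab". Section 4.3 has "SABR will be performed after the second Nivolumab dose but before the fourth dose". Section 5.2 places SABR after the first nivolumab cycle. These statements need to be reconciled in their own right. What matters here is that each of them puts nivolumab first.

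**The concern.** The section that says which patients enter the safety analyses makes inclusion depend on something that happens after treatment has started, namely receiving SABR. Toxicity from the first nivolumab doses can prevent that. Such a patient has been exposed to protocol treatment and has had the event the analysis is meant to count, yet 6.2 leaves the patient out of both numerator and denominator.

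The protocol contains a route by which this could happen. Under 4.2.1.1 a grade 3 or 4 infusion reaction ends nivolumab permanently. If that occurs at the first infusion and SABR is not then given, the patient counts under 4.2.1.1 and 6.1.1 but not under 6.2.

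At stake is the published toxicity rate of the combination. An analyst following 6.2 and one following 6.1.1 could report different rates from the same data, and each could cite the protocol.

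**Working it through.** **Is there a figure to reproduce?** The plan gives no expected toxicity rate and no safety-set size. The only sample-size figure is for response (11.2): 19 patients, plus 2 for dropout, makes 21. It reproduces. An exact binomial test of 25% against 50% at two-sided 0.2 (0.1 in the upper tail) first reaches 80% power at n = 19, with success at 8 or more responses, upper-tail error 0.0775 and power 0.8204. The safety-set question does not change it. The 21 is used below only as a convenient number of treated patients.

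**The three sets compared.** Section 3.0 does not let treatment begin before registration. So 4.2.1.1 and 6.1.1 differ only for patients registered but never treated. The substantive conflict is between those two sections and 6.2, and it concerns patients who received nivolumab but no SABR fraction, or SABR without one nivolumab cycle. A single SABR fraction is enough to satisfy the SABR part of 6.2.

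**Direction of the effect.** Let n patients be treated, x of them with the toxicity of interest. Let k be excluded by 6.2, t of those k with the toxicity.

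- All-treated rate: x/n.
- Rate under 6.2: (x − t)/(n − k).
- The 6.2 rate is the lower one when n(x − t) < x(n − k), that is, when t/k > x/n.

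The rate is therefore understated only when toxicity is more common among the excluded patients than among all treated patients. If every exclusion is due to toxicity, t = k and the condition holds whenever x < n.

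**Size, with assumed counts.** The documents do not say how many patients would stop before SABR, so these are illustrations with n = 21.

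| Assumption | Section 6.2 set | All treated | Difference |
|---|---|---|---|
| 1 excluded, with toxicity; 3 events among the rest | 3/20 = 15.0% | 4/21 = 19.0% | −4.0 points |
| 2 excluded, both with toxicity; 3 events among the rest | 3/19 = 15.8% | 5/21 = 23.8% | −8.0 points |
| 2 excluded, neither with toxicity; 3 events among the rest | 3/19 = 15.8% | 3/21 = 14.3% | +1.5 points |

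Holding the total at 4 events in 21 treated (19.0%), excluding 1, 2 or 3 of the patients with events gives 3/20 = 15.0%, 2/19 = 10.5% or 1/18 = 5.6%.

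**If the excluded patient is also replaced,** so that 21 are analysed and 22 treated, one such patient gives 3/21 = 14.3% against 4/22 = 18.2%. The gap is about the same.

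**The case against.** Several points on the other side have force.

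- **A both-treatments set answers a legitimate question,** namely the toxicity of the combination in those who received it. That stands, but the plan does not label it supportive or set it beside an all-treated rate.
- **The patients are not lost to safety oversight.** Subjects removed for unacceptable adverse events are followed until resolution or stabilisation (4.4). Serious events go to the DSMC (7.5), which reviews them in real time and reviews adverse events quarterly (12.5). None of this is limited to the 6.2 set. This stands, so the point concerns the analysed rate only.
- **The direction is not fixed.** Patients may miss SABR for reasons other than toxicity, as the third row of the table shows. This stands.
- **Replacement after toxicity is one reading, not a settled rule.** The sentence in 5.5.3 sits under inability to comply. Toxicity has its own item, 5.5.5, which does not mention replacement, and the list in 5.6 does not include it. The wording of 5.5.3 is broad enough to cover a patient who missed SABR because of toxicity, but it need not be read so. The exclusion under 6.2 does not depend on replacement.
- **The shift is small beside the uncertainty.** Exact 95% intervals are 3.4 to 39.6% for 3/19 and 8.2 to 47.2% for 5/21, and 11.3 plans no test of the toxicity rate. This limits the consequence but does not remove the contradiction.

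A reader might go further and infer that the 6.2 set drives the six-patient safety review, so that replacing a patient with toxicity takes away one of the four events needed for a hold. The documents do not support that. Sections 7.8 and 11.2 both define the cohort as the first six patients assigned, and neither refers to 6.2 or to replacement. Section 11.2 also counts only serious events attributed to the combination, so how an event before SABR would be attributed is a separate question.

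**Conclusion.** The plan is wrong as written. Section 6.2 contradicts 4.2.1.1 and 6.1.1 on who is analysed for safety, and 11.3 does not settle it. If 6.2 is followed, treated patients whose toxicity prevents SABR are left out of the toxicity rate. In the illustrations this understates the rate by 4.0 points for one such patient and 8.0 points for two.

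The contradiction rests on the text alone. The size rests on assumed counts, and the downward direction holds only when toxicity is more common among the excluded patients than among all treated patients. The conclusion does not extend to serious adverse event reporting, to the six-patient hold rule or to the sample size of 19 (21 with dropouts).

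**What to change.** 1. State one safety set, **all patients who received any nivolumab or any SABR fraction**, in the same words in 4.2.1.1, 6.1.1 and 6.2, and name it in 11.3 as the denominator of the toxicity rate.
2. State that replacement under 5.5.3 or 5.6 does not remove a treated patient from this set. Make clear that the inclusion sentence in 5.5.3 does not define the safety set.
3. Report toxicity in the SABR-plus-nivolumab subset as a supportive analysis, and give the number of treated patients outside it with their reasons for not receiving SABR.
4. For the six-patient review, keep the first six assigned as 7.8 and 11.2 have it, and add only that replacement does not remove a treated patient from that count.

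The cost is a few sentences of wording. Sample size and treatment do not change. The downside is that the reported toxicity rate may be slightly less favourable.
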